5. REGISTRATION AND RANDOMISATION

Direct line for 24-hour registration & randomisation: [name]

Recruitment to PICCOLO is a 2-step process:

1. Registration: an initial introduction to the trial is given and written assent for *K-RAS* testing is obtained. A PICCOLO trial ID number will be assigned to the patient at this stage.
2. Randomisation: a full explanation of the trial including detailed information about the rationale, design and personal implications of the study is given and formal consent to randomisation is obtained. At this stage the treatment allocation will be determined.

The minimum interval between these stages is 24 hours, but this will apply only to patients whose *K-RAS* status has been previously determined. Most patients will require *K-RAS* testing during this time, so the normal interval will be 1-2 weeks.

A record of the consent processes detailing the date of consent and all those present will be kept in the patient notes. Both the *K-RAS* Testing and PICCOLO Consent Forms must be signed by an authorised medically qualified person. The right of the patient to refuse consent without giving reasons will be respected. Further, the patient will remain free to withdraw from the study at any time without giving reasons and without prejudicing any further treatment. The original consent forms should be filed in the Investigator Site File, a copy should be given to the patient and a further copy of the consent form should be sent to the Clinical Trials Research Unit (CTRU) at the University of Leeds. A copy of the Patient Information Sheet and Consent Form document should be filed in the patient hospital notes if required.

Participating centres will register and randomise patients using the 24-hour automated registration/randomisation system based at the CTRU. A centre code, authorisation code and PIN, which will be provided by the CTRU, will be required to access this system. These codes will only be issued once a centre has been fully approved and all the necessary documentation has been received. Precise details of documentation required prior to the start of recruitment at each centre will be outlined on expression of interest from participating centres.

5.1 Registration

When a patient is identified who may potentially be suitable for PICCOLO a verbal introduction to the trial is given and the *K-RAS* Testing Patient Information Sheet/Consent Form is provided and sufficient time allowed for the patient to consider it. In some cases, the clinician or research nurse may feel it more appropriate to arrange an extra visit to obtain written consent for *K-RAS* testing. It is made clear to the patient that this is not consent to participate in the PICCOLO trial:

they remain free to decide not to participate, or they may be found to be ineligible after the formal eligibility assessment.

Please note that it is acceptable for a patient currently receiving first-line chemotherapy to register and consent for *K-RAS* testing if the treating consultant feels that PICCOLO may be a suitable option for the patient in the future. In this case, the *K-RAS* result will be held at the CTRU and if the patient subsequently decides to take part in PICCOLO there will be no delay to commencing trial treatment whilst waiting for the *K-RAS* result.

When the patient has provided written consent for *K-RAS* testing, the research nurse will:

1. Call the registration line. A trial number will be allocated to the patient.
2. Ascertain the hospital(s) where previous colorectal cancer surgery was performed (e.g. the primary cancer resection), and obtain histology report(s) and sample number(s)
3. Contact the relevant histology department(s) to establish that they have tumour tissue blocks* and explain that they are needed urgently.
4. Fax the completed '*K-RAS* Sample Request Form' and a copy of the completed consent form to the histology department, with a copy of the same documents faxed to the CTRU.

**If the patient has previously participated in a clinical trial (e.g. COIN), tissue blocks may already be in a research lab. If this is the case, please contact the CTRU who will arrange direct transfer. If any other difficulties are encountered (eg histology department unable to release blocks) please contact the CTRU immediately.*

The '*K-RAS* Sample Request Form' includes instructions for the histology department sending the tissue blocks to the DNA laboratory. In most cases this will be:

PICCOLO Trial Laboratory
Gastrointestinal Cancer Translational Research,
Leeds Institute of Molecular Medicine,
[name],
St James's University Hospital,
[name].

However, in some cases Units may have alternative arrangements for EGFR testing.

K-RAS mutation status will be notified directly from the PICCOLO Trial laboratory to the CTRU as soon as it is available.

Average turn-around from arrival of tissue blocks in the research laboratory is 4-5 working days: this and the time taken to retrieve the blocks should be taken into consideration when arranging the consent to participation in the trial/ randomisation visit (approx. 2 weeks in total).

K-RAS result

Please note that the *K-RAS* result will be held in confidence by the CTRU and will not be made known to the site or patient.

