In April 2008, published data from a large RCT showed convincingly that patients with *K-RAS* wild-type tumours gained prolongation of progression-free survival if randomised to receive panitumumab, but patients whose tumours had mutated *K-RAS* gained no benefit.³⁴ This interaction was significant at $p < 0.0001$, suggesting that *K-RAS* is a potentially valuable predictive biomarker for panitumumab. These findings have now been validated by data from three further RCTs showing that whilst patients with wild-type *K-RAS* tumours may benefit from either panitumumab or cetuximab, patients with mutated *K-RAS* tumours do not.^{35,36,37} In *KRAS*-mutation patients receiving oxaliplatin +/- bevacizumab, addition of an anti-EGFR drug was observed to shorten the time to progression, suggesting a possible antagonistic interaction^{35,37} but this was not seen in trials of anti-EGFR drugs alone or in combination with irinotecan.^{34,36}

Given this new information, the PICCOLO Trial Management Group, in consultation with the NCRI Colorectal Clinical Studies Group and independent Trial Steering Committee, decided to modify the PICCOLO trial design from mid-2008. This decision was made for two reasons:

- With the weight and consensus of evidence now suggesting that patients with *K-RAS*-mutated tumours cannot benefit from anti-EGFR mAb, it is important to avoid patients in this group being exposed to panitumumab and risking its adverse effects with no realistic prospect of benefit.
- The future development of anti-EGFR monoclonal antibody therapy in colorectal cancer will be restricted to patients with demonstrable *K-RAS* wild-type tumours. Therefore, the principal question addressed by the PICCOLO trial, whether the addition of panitumumab to irinotecan improves survival in patients with colorectal cancer, must now be up-dated to whether the addition of panitumumab to irinotecan improves survival *in patients with K-RAS-wild-type* colorectal cancer.

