anticipate to be around 15%). This will be monitored throughout the study as this may vary. In order to achieve the required number of patients for each comparison we will recruit approximately 1324 patients in total (494 already recruited under Protocol Version 1; 830 using Protocol Version 2, assuming 15% of patients with unknown *K-RAS* status, and 15% of patients have previously received anti-EGFR targeted therapy).

Patients randomised using the previous version of the protocol, without advance knowledge of *K-RAS* status, will have their *K-RAS* status determined retrospectively (provided consent has been obtained for tissue retrieval), and will be incorporated in the relevant treatment comparisons as detailed in Section 11.

In addition, approximately 86 anti-EGFR targeted therapy pre-treated patients who have wild-type *K-RAS* status will be available for an assessment of the efficacy of **Ir** versus **IrPan** in this pre-treated group. Similarly, patients randomised to Ir or IrPan using the previous version of the protocol, who are retrospectively found to have mutant or unknown *K-RAS* status, will be available for an assessment of the efficacy of **Ir** versus **IrPan** in this group of patients

All PICCOLO patients are studied for clinical and pharmacogenetic endpoints. All patients are also invited to donate any surplus stored formalin-fixed paraffin-embedded (FFPE) tumour samples for translational research. A pharmacokinetic (PK) Sub-study is being undertaken in 20 patients randomised to IrCs at centres with appropriate facilities in order to compare Ir, SN38 and SN38G pharmacokinetics after Ir or IrCs treatment.

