6.3 Treatment Duration & Treatment Breaks

- The initial treatment period is 12 weeks followed by clinical and radiological re-assessment
- Patients with clinical benefit (radiological and symptomatic response or stabilisation) will be offered further treatment until disease progression or toxicity

- After the initial 12 weeks patients with stable or responding disease may have a planned treatment break of up to 6 weeks (i.e. omit up to 2 cycles of treatment, re-starting up to 9 weeks after the last irinotecan dose). In this event please note:
 - a) there is no change in the scanning schedule i.e. patients should be scanned at 24, 36, 48 weeks etc post randomisation until progression
 - b) patients on IrPan should continue to receive Pan as a single agent during the treatment break (see section 6.2.5)
 - c) If clinical or radiological progression emerges during a break, the patient should resume their allocated treatment, provided that the treating consultant considers this to be in the patient's best interest. Patients on the IrPan arm who have received single-agent Pan during the break should re-start IrPan.

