6.5 Cross-over

- Crossover involving ciclosporin:
 - Cross-over from **IrCs** to **Ir** should be avoided if possible, however if a patient cannot tolerate Cs this may be necessary. Please inform the CTRU.
 - the half-life of Cs is around 6 hours in most patients but may be as long as 20 hours. Therefore at least 1 week wash-out time must be allowed after the patient took their last Cs dose, before they receive standard-dose Ir.
 - Cross-over from **Ir** or **IrPan** to **IrCs** is not permitted
- Crossover involving Panitumumab:
 - Cross-over from **IrPan** to **Ir** should be avoided if possible, however if a patient cannot tolerate Pan this may be necessary. Please inform the CTRU.
 - Cross-over from **Ir** or **IrCs** to **IrPan** is not permitted.

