6.10 Withdrawal of Treatment

In line with usual clinical care, cessation or alteration of regimens at any time will be at the discretion of attending clinicians or the patients themselves. All patients withdrawn from treatment or prescribed an alternative treatment will still attend for follow-up assessments unless unwilling to do so and Case Report Forms will continue to be completed.

If a patient explicitly states they do not wish to contribute further data to the study the CTRU should be informed in writing.

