Since previous anti-EGFR targeted therapy use is of no concern for the Ir vs. IrCs comparison, this analysis will include all patients randomised to receive either Ir or IrCs under Protocol Version 1.0, and all patients randomised to receive either Ir or IrCs via the Ir vs. IrCs randomisation in this amended protocol, regardless whether or not they have previously used anti-EGFR targeted therapy.

The two primary comparisons of Ir vs. IrCs and Ir vs. IrPan are essentially two independent comparisons⁴¹. We therefore aim to recruit 480 patients who have wild-type *K-RAS* status and who have not previously received an anti-EGFR targeted therapy (240 patients per arm) to the Ir vs. IrPan comparison. However, dependent upon the proportion of patients with unknown *K-RAS* status, there may be some over-recruitment to this comparison. We expect approximately 15% of all patients recruited to this comparison to have previously received an anti-EGFR targeted therapy therefore the expected sample size for the exploratory analysis of Ir vs. IrPan for those patients previously receiving an anti-EGFR targeted therapy (and who have wild-type *K-RAS* status) is approximately 86 patients (43 patients per arm of Ir/IrPan).

K-RAS status

We expect that the split between mutant *K-RAS* status and wild-type *K-RAS* status will be approximately 42:58, and that approximately 15% of patients will have unknown *K-RAS* status. The proportion of patients with unknown status will be monitored as this figure may vary. Only patients with wild-type *K-RAS* status will be randomised to the Ir vs. IrPan comparison. There will, however, be some patients randomised to IrPan via protocol Version 1.0 who will have either mutant or unknown *K-RAS* status. We anticipate that approximately 167 mutant or unknown *K-RAS* status patients will have been randomised to receive either Ir or IrPan under Protocol Version 1.0, of whom approximately 19 will have previously received an anti-EGFR targeted therapy. An exploratory analysis will be carried out on these patients.

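### Section 5.1 withholds the K-RAS result without exception, so a Version 1 IrPan patient later found mutant may stay on panitumumab without the treating clinician being told

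*Protocol*

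**What the plan says.** Section 5.1 routes the result to the trials unit alone: "mutation status will be notified directly from the PICCOLO Trial laboratory to the CTRU as soon as it is available". It then states that the result "result will be held in confidence by the CTRU and will not be made known to the site or patient". No exception follows there or elsewhere.

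Section 3 says that patients randomised under the previous version, without advance knowledge of K-RAS, will have their "status determined retrospectively (provided consent has been obtained for tissue retrieval"). It describes this testing in the present tense, as under way. Section 11.1 accepts what the testing will find: "There will, however, be some patients randomised to IrPan via protocol Version 1.0 who will have either mutant or unknown" K-RAS status. The uses the protocol gives for these results are assignment to the treatment comparisons and a descriptive exploratory analysis (sections 2, 3, 11.1 and 12).

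On continuing treatment, section 6.3 says: "Patients with clinical benefit (radiological and symptomatic response or stabilisation) will be offered further treatment until disease progression or toxicity". Section 6.5 says that crossing from IrPan to Ir "should be avoided if possible, however if a patient cannot tolerate Pan this may be necessary". Section 6.10 adds that "cessation or alteration of regimens at any time will be at the discretion of attending clinicians or the patients themselves".

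Section 1 gives, as the first reason for the redesign, that for patients with mutated tumours "it is important to avoid patients in this group being exposed to panitumumab and risking its adverse effects with no realistic prospect of benefit".

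**The concern.** The redesign acts on its safety reason only through allocation, and allocation protects only patients tested before randomisation. Version 1 patients had already been allocated. If one of them on IrPan proves mutant, the trials unit holds the very fact that the protocol treats as decisive, while the clinician who decides on the next infusion does not have it.

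The treatment rules favour continuing. Therapy runs to progression or toxicity, panitumumab is given alone during planned irinotecan breaks (sections 6.2.5 and 6.3), and intolerance is the only ground section 6.5 gives for leaving it.

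What is at stake is toxicity without benefit. In the monotherapy trial tabulated in section 1, 95% of patients had skin toxicity and 7% had it at grade 3. The concern does not rest on panitumumab worsening tumour control: section 1 reports possible antagonism with oxaliplatin-based treatment, but not with irinotecan.

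**Working it through.** **1. Does any provision release the result?**

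| Place in protocol | What it provides |
|---|---|
| 5.1 | Laboratory reports to the trials unit; site and patient not told |
| 5.2 | Mutant or unknown patients are randomised to Ir or IrCs; applies to new patients only |
| 6.3, 6.4 | Continue to progression or toxicity; dose changes for toxicity; no K-RAS stopping rule |
| 6.5 | IrPan to Ir to be avoided; intolerance is the stated reason |
| 6.10 | Clinician or patient may stop at any time; no route to the result |
| 8 | Safety reporting; no K-RAS disclosure |
| 12.1 | DMEC reviews the proportion with unknown status, not individual mutant results |

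None releases a retrospective mutant result. Under the new design, allocation to IrPan implies wild-type, so the clinician can infer the status. Under Version 1, allocation carries no such information.

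**2. Reproducing the protocol's own figure.** Inputs: 494 patients recruited under Version 1 (11.2); 329 of them on Ir or IrCs (3); equal allocation to three arms (1); 15% unknown and a 42:58 mutant to wild-type split (11.1).

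- Mutant or unknown share = 1 − 0.85 × 0.58 = 0.507.
- Version 1 patients on Ir or IrPan = 2/3 × 494 = 329.
- 329 × 0.507 = 166.8, against about 167 stated in 11.1. The figure reproduces.

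**3. Size of the group.**

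- Version 1 IrPan = 494 − 329 = 165.
- Mutant share = 0.85 × 0.42 = 0.357.
- Expected mutant on IrPan = 165 × 0.357 = 58.9, about 59. With the 30% to 50% mutation range in section 1 and 15% unknown, this is 42 to 70.

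**4. How many might still be on treatment (illustration).** The protocol gives neither time on treatment nor the dates of results. Assume uniform accrual over 18 months (opened December 2006, design changed mid-2008, 18 months of a 3-year target remaining) and exponential time on treatment with median m, so k = ln 2 / m. The fraction on treatment d months after the changeover is

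(1 − e^(−18k)) / (18k) × e^(−kd).

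The central m of 4.2 months is borrowed from the irinotecan PFS in 11.1.

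| Median m (months) | Fraction, d = 0 | Patients of 58.9 | Fraction, d = 3 | Patients of 58.9 | d = 3, 80% consented |
|---|---|---|---|---|---|
| 3 | 0.237 | 13.9 | 0.118 | 7.0 | 5.6 |
| 4.2 | 0.319 | 18.8 | 0.195 | 11.5 | 9.2 |
| 6 | 0.421 | 24.8 | 0.298 | 17.5 | 14.0 |

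The consent rate for tissue retrieval is not given; 80% is an assumption, and some non-consent may already be counted in the 15% unknown.

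**5. Effect of disclosure on the exploratory endpoint.** The fraction on treatment and less than 12 weeks (2.76 months) from randomisation at the changeover is (1 − e^(−2.76k)) / (18k) = 0.113, 0.123 and 0.131 for the three medians, or 6.7, 7.3 and 7.7 patients. It is zero once 12 weeks have passed since the last Version 1 randomisation.

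**The case against.** The strongest reply is that the confidentiality sentence belongs to the registration procedure for new patients and does not mention Version 1 patients, whose testing is described elsewhere with no such clause. That is true of its position. But its wording is unqualified, no other rule covers the older cohort, and on either reading nothing releases the result.

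Release may have been arranged in a letter or information sheet that is not shown. This stands, and it is why the conclusion says that patients *may* remain on the drug. Such a letter would still conflict with 5.1 as worded.

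Clinicians treat open-label, know the K-RAS evidence from section 1, and can stop at any time under 6.10. Section 5 also recognises that K-RAS status may already be known for some patients. But discretion is of little use without the result, and the protocol sets up no outside testing for these patients while the trials unit already holds the answer. The DMEC's safety reviews look for patterns, not individual genotypes.

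The counts still on treatment are assumptions. This stands. Treatment stops at progression or toxicity, so the 6-month median is generous. Section 1 also marks its K-RAS text as added for Version 3.0, so the present text may postdate the changeover and fewer patients may remain.

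Telling sites only of mutant results lets them infer that a tested IrPan patient without a letter is wild-type or unknown, and the wild-type patients without prior anti-EGFR therapy are in the primary survival comparison. This is a real but probably small cost; under the new design every IrPan allocation already reveals wild-type status. Whether Version 1 consent covers return of individual results also needs checking.

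**Conclusion.** The concern holds. Followed as written, the protocol can leave a patient known by the trials unit to be mutant on panitumumab, against the first reason it gives for the redesign. About 59 Version 1 IrPan patients are expected to be mutant, using inputs that reproduce the protocol's 167. The number still exposed is uncertain: about 19 (14 to 25) at the changeover, about 11 (7 to 18) three months later, and about 9 (6 to 14) if in addition 80% consented, all resting on assumed accrual and time on treatment.

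Mutant Version 1 IrPan patients are outside the primary Ir versus IrPan comparison, which is restricted to wild-type, and IrPan patients are outside Ir versus IrCs. No primary endpoint, power or type I error is at issue. It should be corrected for patient safety, and even a handful of affected patients would justify it.

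**What to change.** Add to section 5.1:

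> This confidentiality rule does not apply to patients randomised to IrPan under Protocol Version 1.0 who are still receiving panitumumab. These patients will be tested first. The CTRU will promptly inform the treating clinician of a mutant result so that continuation of panitumumab can be decided under section 6.10. The reason for any change is recorded on the existing treatment forms, and the patient is analysed as randomised.

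Before use, confirm that the Version 1 consent permits an individual result to be returned, and seek consent where it does not.

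The cost is four sentences and letters to a small number of sites. Testing is already under way, and the treatment forms already capture dose changes and their reasons (7.5). Some IrPan exposure would be shortened in the mutant/unknown exploratory analysis, which is descriptive. Only about 7 of the 59 would be on treatment and still short of their 12-week endpoint at the changeover, and none later than 12 weeks after the last Version 1 randomisation.

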5.2 Randomisation

A verbal explanation of the PICCOLO Patient Information Sheet and Consent Form document will be provided by the attending hospital staff for the patient to consider and a paper copy provided to the patient. This will include detailed information about the rationale, design and personal implications of the study. Following information provision, patients will have as long as

they need to consider participation (normally a minimum of 24 hours) and will be given the opportunity to discuss the trial with their family and healthcare professionals before they are asked whether they would be willing to take part in the trial. After the patient has provided written informed consent and has been confirmed as eligible the patient may be randomised.

Patients who fulfil the eligibility criteria, and have given signed informed consent, and whose *K-RAS* status has been determined as **mutation**, or whose *K-RAS* status is **unknown**, will be randomised on a 1:1 basis to receive either standard **Ir** or **IrCs**.

Patients who fulfil the eligibility criteria, have given signed informed consent, and whose *K-RAS* status has been determined as **wild-type** and **have not** previously received an anti-EGFR targeted therapy will be randomised on a 1:1 basis to receive either standard **Ir** or **IrPan**.

Patients who fulfil the eligibility criteria, have given signed informed consent, and whose *K-RAS* status has been determined as **wild-type** and **have** previously received an anti-EGFR targeted therapy will be randomised separately on a 1:1 basis to receive either standard **Ir** or **IrPan**.

Randomisations will be achieved using dynamic allocation incorporating a random element, via a computer-generated programme, to ensure treatment groups are well-balanced for the following patient characteristics, details of which will be required for randomisation:

- Randomising centre
- Previous treatment with oxaliplatin (no –vs– yes)
- Previous treatment with bevacizumab (no –vs– yes)
- Best response to any previous drug therapy (response/stable disease –vs– progressive disease alone –vs– unknown)
- Required dose reduction or delay for toxicity during previous therapy (yes –vs– no)
- WHO performance status (0 or 1 –vs– 2)

The person telephoning to randomise the patient should have the completed Randomisation Checklist in front of them at the time of telephoning as the following additional information will be required at randomisation:

- Patient's 5 digit trial no assigned at registration
- authorisation code and PIN
- basic patient details including initials, date of birth, hospital number, weight
- name of centre and centre code
- name of consultant and person making randomisation
- confirmation of eligibility (including date of written informed consent)

NB. The patient should be asked to complete the baseline quality of life questionnaire prior to randomisation.

